11.2. Study Candidate Screening

The investigator or designee is responsible for screening potential patients and selecting those who meet all inclusion criteria and do not meet any of exclusion criteria.

11.3. Informed Consent

Subjects who meet all of the inclusion criteria, none of the exclusion criteria, and sign and date the informed consent form are considered enrolled in the study.

11.4. Enrollment Visit

The Enrollment Visit may occur at the pre-discharge visit, and must be between 1 day and 21 days after the CRT-D implantation procedure. Enrollment cannot occur on the same day of the implantation procedure. A list of the data to be collected at the Enrollment Visit is provided below, with further details included in the sections below.

- CRT-D indication verification
- Echo measurement
- Subject demographics
- Medical history and medications
- NYHA class assessment
- Device and lead information
- Current device settings and status
- Lead measurements
- SmartDelay test and value
- Asense to Vsense and Apace to Vsense intervals
- LV VectorGuide test and value
- RVp-LVs interval test
- LV lead location (if available)
- Battery consumption
- Sleep Incline Trend calibration
- Final device settings and status
- Adverse event assessment

11.4.1. CRT-D Indication Verification

The following values from the subject's medical record are required to demonstrate that each subject met BSC's labeled indications prior to their CRT-D implantation:

- Most recent Echo measurement of LVEF and date of measurement
 - It is required that the LVEF value be measured no more than 6 months prior to the CRT-D implantation.
 - The following measurement will be collected per site’s standard of care practice: LVESV, LVEDV, Aortic VTI, and Mitral valve regurgitation.
- QRS duration
- Bundle Branch Block morphology (LBBB or non-LBBB)
- Heart failure etiology (ischemic or non-ischemic)
- NYHA class value
- Cardiovascular medications

11.4.2. Subject Demographics

Subject’s age, sex, and race/ethnicity are required.

11.4.3. Medical History and Medication

Subject’s history of cardiovascular diseases and current cardiovascular medications use are required to be collected.

11.4.4. NYHA Class Assessment

Obtain the subject’s most recent NYHA Class assessment prior to the CRT-D implantation per the definition shown in **Table 11.4-1**.

Table 11.4-1: NYHA Classifications⁵

Class	Patient Symptoms
I	No limitation of physical activity. Ordinary physical activity does not cause undue fatigue, palpitation, dyspnea (shortness of breath).
II	Slight limitation of physical activity. Comfortable at rest. Ordinary physical activity results in fatigue, palpitation, dyspnea (shortness of breath).
III	Marked limitation of physical activity. Comfortable at rest. Less than ordinary activity causes fatigue, palpitation, or dyspnea.
IV	Unable to carry on any physical activity without discomfort. Symptoms of heart failure at rest. If any physical activity is undertaken, discomfort increases.

⁵ NYHA Heart Failure Classification by American Heart Association, updated September 28, 2016. http://www.heart.org/HEARTORG/Conditions/HeartFailure/AboutHeartFailure/Classes-of-Heart-Failure_UCM_306328_Article.jsp#.WLWhqUrKpo

11.4.5. Device Information

The following are required for the implanted CRT-D device, RA lead, RV lead, and LV lead:

- Manufacturer
- Model and serial number
- Implant date

11.4.6. Current Device Settings and Status

Print a copy of the Quick Notes Report from the PRM to document current device settings and status prior to conducting any test and changing the programming settings.

11.4.7. Lead Measurements

The following lead measurements are required to be collected for the RA lead, RV lead, and LV lead:

- Intrinsic amplitude (mV)
- Pacing capture threshold (PCT in V; the recommended pulse width is 0.4 ms)
- Pacing lead impedance (Ω)
- Shocking lead impedance (Ω , RV lead).

The following document is required for the RA lead, RV lead, and LV lead measurements:

- Print a copy of the Quick Notes Report from the PRM

Lead measurement testing is required unless a rationale is provided. For example, the measurement is prohibited by a subject's condition.

It is recommended that the PCT measurements be collected in the following fashion:

- At least 3 cardiac cycles at a given voltage level are obtained before stepping down to the next voltage level.
- A count of two non-capture beats at a given voltage level is reached before declaring a loss of capture (LOC) for any of these tests.
- The pacing configurations used in the LV lead measurement testing are per the investigator discretion. At least one configuration must be tested for the LV lead, and it is recommended that the tested configuration be the configuration planned for final programming.

It is recommended that the threshold be defined as one voltage level above the level where two non-captured beats are observed. If multiple PCT tests were performed, only the final measurement is required to be entered on the CRF.

11.4.8. SmartDelay Test

It is required to perform the SmartDelay test for all subjects to obtain programming recommendations for the AV Delay and Pacing Chamber. It is per the investigator discretion whether to follow the programming recommendations. However, the Pacing Chamber that is selected for a subject at the Enrollment Visit must be used for that subject through the 6 Month Visit (for all subjects) and through the 12 Month Visit (for non-responders).

The LV offset is required to be set at 0 ms prior to running the SmartDelay test.

The SmartDelay test nominal Temporary Paced Lower Rate Limit (LRL) is set at 80 bpm. It is recommended to set the LRL at 10 to 15 bpm above the subject's intrinsic heart rate before conducting the SmartDelay test.

The following values from the SmartDelay test are required to be collected:

- SAV (sensed AV delay) and PAV (paced AV delay), both the recommended and final programmed values.
- Pacing Chamber (BiV or LV Only), both the recommended and final programmed values.
- Rationale if the SmartDelay recommendations are not followed.

The following documents from the SmartDelay test are required:

- Set EGM channels to RA, RV, and LV. Obtain ECG/EGM strips at the paper speed of 100 mm/s for approximately 3-5 representative beats during the Atrial Sense test and Atrial Pace test, respectively. The following values are required to be measured from the ECG/EGM strips:
 - Asense-RVsense, Asense-LVsense, Apaced-RVsense, and Apaced-LVsense intervals for each of the representative beats
 - Calculate the mean value for each of the 4 intervals from these representative beats

Record the Subject ID and visit information (Enrollment, 6 Month, or 12 Month) on each ECG/EGM strip. Copies of all ECG/EGM strip should be submitted to BSC quarterly or more frequently, and before study ends. The data collected in this test will be used for future product feature enhancement or development, and are not associated with the primary and ancillary objectives. A deviation is not required if the ECG/EGM strips are not sent to BSC.

- Print a copy of the Settings Changes Report from the PRM immediately after running the SmartDelay test and before any other changes in settings are made and programmed. This report will display the recommended changes to the SAV, PAV, and Pacing Chamber at pending status.

If the SmartDelay test fails to complete, re-perform the test to obtain the recommended value. If the SmartDelay test was complete but not successful, the SmartDelay will display the nominal value as the recommended value. The SmartDelay test should be limited to two attempts in total.

11.4.9. LV VectorGuide Test

It is required that the RV-LV interval value be measured from all 4 electrodes as cathode (LVTip1, LVRing2, LVRing3, and LVRing4) by starting the LV VectorGuide Test; however, it is not required to complete all steps of the LV VectorGuide test once the RV-LV intervals are collected. If the LV VectorGuide test is completed, provide the number of viable pacing vectors (See **Section 8.2** for definition of viable pacing vectors).

Subjects must have RV and LV sensed beats for test to be successful. If the subject does not tolerate a low intrinsic heart rate, stop the test and provide the rationale for not completing the required test (e.g. subject needs RV pacing support).

The following values are required to be collected:

- Select the unipolar vectors and run the RV-LV Delay test for all 4 unipolar vectors to obtain RV-LV delay values.

The following values are required to be collected only if the LV VectorGuide test is completed:

- Number of viable pacing vectors (See definition in **Section 8.2**)

The following document is required:

- Print a copy of the LV VectorGuide Report from the PRM.

11.4.10. RVp-LVs Interval Test

The data collected in this section will be used for future product feature enhancement or development, and are not associated with the primary and ancillary objectives. A deviation is not required if the test is not performed or the ECG/EGM strips are not sent to BSC.

Set the EGM channels to RA, RV and LV, pacing mode to VVI, LRL to 10 to 15 beats above the subject's intrinsic rate and ventricular pacing chamber to RV Only. Obtain the ECG/EGM strips at the paper speed of 100 mm/s for approximately 3-5 representative beats in two LV sense vector configurations: LVTip1 to Can and LVRing2 to Can, respectively. Record the Subject ID, visit information (Enrollment, 6 Month, or 12 Month), and the cathode of the LV sensing configuration (LVTip1 or LVRing2) on each ECG/EGM strip. Copies of all ECG/EGM strip should be submitted to BSC quarterly or more frequently, and before study ends.

11.4.11. LV Lead Location

The coronary venous LV lead location is required to be collected if the location information is available; such information would typically be available by reviewing lead imaging documents including in-procedure fluoroscopy or pre-discharge chest X-rays, or obtained from the subject's medical record.

The LV lead location is required to be classified and recorded in the eCRF as follows:

- Anterior, anterolateral, lateral, posterolateral, or posterior
and

- Basal, Middle, or Apical

11.4.12. Battery Consumption

The following values are required to be collected:

- Time to explant
- Charge Remaining

11.4.13. Sleep Incline Trend Calibration

The Sleep Incline Trend of the CRT-D device will be calibrated at Enrollment Visit. Calibration is not required if the Sleep Incline Sensor is initializing or if the trend is already calibrated prior to this visit. The data collected in this section will be used for future product feature enhancement or development, and are not associated with the primary and ancillary objectives. A deviation is not required if the calibration is not performed.

11.4.14. Final Device Settings and Status

Print a copy of the Device Settings Report from the PRM for all subjects at the Enrollment Visit and clear the device counters as the final step. Record whether the HeartLogic feature (Heart Failure Sensor Suite) is enabled in the CRT-D device and whether the HeartLogic Alert is programmed ON via the LATITUDE system. All subjects at the Enrollment Visit are required to receive conventional CRT therapy and have the LV MSP feature programmed off. All other programming settings are per investigator discretion.

11.4.15. Adverse Event Assessment

Study required adverse event data will be collected and assessed for each subject after signing of the informed consent. See **Section 20** for Adverse Event collection and reporting requirements.

A summary of the source documentation required at the Enrollment Visit is described in **Table 11.4-2**.

Table 11.4-2: Source Documentation Required at Enrollment Visit

Source Documentation Requirement	Disposition
Informed consent form and process, including informed consent signature and date	Retain at study site
Inclusion and exclusion criteria	
Cardiovascular disease history and medication	
NYHA class assessment	
Device and lead information	
Adverse event assessment	
Device Settings Report, Quick Notes Report, LV VectorGuide Report, Settings Changes Report	
Echo measurement, if performed per standard of care	
Manually recorded Charge Remaining	
ECG/EGM Strips from the SmartDelay test	Retain at study site Submit 1 copy to BSC
ECG/EGM Strips from the RVp-LVs interval test	

11.5. 6 Month Visit

The 6 Month Visit must be performed in office at 183 -30 days/+0 day post-Enrollment Visit. A list of the data to be collected at the 6 Month Visit is provided below, with further details included in the sections below.

- NYHA class assessment
- Patient Global Assessment
- Physician Global Assessment
- HF event
- Response status determination
- Echo measurement
- Current device setting and status
- Lead measurements
- LV VectorGuide test and value
- RVp-LVs interval test
- SmartDelay test and value

- Asense to Vsense and Apace to Vsense intervals
- SmartVector and SmartOffset value
- Battery consumption
- Final device settings and status
- Adverse event assessment
- HeartLogic Alert
- “Save All” device data

11.5.1. Definition and Components of the Clinical Composite Score

The CCS will be calculated for all subjects at the 6 Month Visit. The CCS consists of the following components:

- All-cause mortality
- Heart Failure (HF) event
- Patient Global Assessment (PGA)
- NYHA class

11.5.1.1. HF Event Definition

For the purpose of the CCS calculation, HF event is defined as an adverse event with a primary cause of HF and either of the conditions below is met:

- Subject is admitted and discharged with a calendar date change.
- Subject is not hospitalized but received one or more IV medications including diuretics, inotropes, vasodilators, other parenteral therapy, or aquapheresis.

11.5.1.2. PGA Classification

Interpretation of no change status in PGA is defined as the following:

- A little better, no change, and a little worse.

Per CCS definition, a little better and a little worse are considered placebo effect and are treated as no change in PGA status.

The investigator will use the subject’s response to the PGA and classify response of “a little better”, “no change”, or “a little worse” to the category of “no change”. Subsequently, the investigator will use “very much better”, “much better”, “no change”, “much worse”, and “very much worse” to determine the status of PGA changes.

See **Table 11.5-1** for a detailed description of the PGA assessment tool.

11.5.1.3. NYHA Class Assessment

See Section 11.4.4 for a detailed description of performing NYHA Class assessment.

11.5.1.4. CCS Status Classification

Subjects will be classified as improved, unchanged, or worsened by comparing their clinical response in the current visit to their last visit. At the 6 Month Visit, subjects' status will be compared to their status immediately prior to receiving the CRT-D implantation. The following criteria will be used:

- Improved: Subjects are considered improved if they experienced a favorable change in at least one NYHA functional class or in the PGA (or both) while remaining alive and free of HF event comparing to their status in the Enrollment Visit. See **Table 11.5-1** on selecting improved PGA status.
- Worsened: Subjects are considered worsened if any of the followings occurs:
 - died (from any cause) or
 - experienced an HF event or
 - reported worsening of at least one NYHA functional class or
 - reported worsening of the PGA comparing to their status immediately prior to receiving the CRT-D implantation. See **Table 11.5-1** on selecting worsened PGA status.
- Unchanged: Subjects are considered unchanged if they are neither improved nor worsened.

11.5.2. NYHA Class

NYHA Class assessment shall be performed by a site staff who is blinded to the study design, subject's clinical status in the study, and the programmed device settings. The subject's current NYHA Class must be determined based on **Table 11.4-1**.

11.5.3. Patient Global Assessment

The current PGA must be filled out by the subject, as specified in the assessment tool in **Table 11.5-1**.

11.5.4. Physician Global Assessment

The current Physician Global Assessment (PhGA) will be filled out by the investigator/delegated site staff based on the evaluation of the subject's status from multiple clinical aspects. A comparison of the assessment tool for the PGA and PhGA is shown in **Table 11.5-1**.

Table 11.5-1: Comparison of the Global Assessment Tool: Patient Global Assessment (PGA) and Physician Global Assessment (PhGA)

Patient Global Assessment: Check the response which best describes how you feel today compared to prior to the CRT-D implantation (asked at the 6 Month Visit) or compared to the 6 Month Visit (asked at the 12 Month Visit).

- Very much better
- Much better
- A little better
- No change
- A little worse
- Much worse
- Very much worse

Physician Global Assessment: How is the patient's clinical status today compared to his or her status at prior to the CRT-D implantation (assessed as the 6 Month Visit) or compared to the 6 Month Visit (assessed at the 12 Month Visit).

- Markedly improved
- Moderately improved
- Mildly improved
- No change
- Mildly worse
- Moderately worse
- Markedly worse

11.5.5. Response Status Determination

Based on subject's vital status, NYHA class, PGA, and occurrence of HF event, the investigator/delegated site staff will classify each subject to either responder or non-responder per the following criteria:

- Responder: subjects with an Improved CCS score
- Non-Responder: subjects with a Worsened or unchanged CCS score

The PhGA will not be used in classifying the subject response status. Responders will complete the study at the end of their 6 Month Visit based on the CCS status collected on the 6 Month Visit eCRF.

All reported hospitalizations and events that meet the definition of HF events will be adjudicated by the Clinical Events Committee (CEC) for relatedness to the heart failure. A subject with any hospitalization or IV therapy reported in the first 6 months will continue to be followed as a non-responder, regardless of the CCS. If the CEC determines that the event is not an HF event and the subject belongs to the Responder Group, the subject will be exited prior to the 12 Month Visit and excluded from the analysis for the non-responders.

Non-responders will continue to be followed in the study via the Non-Responder Group.

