10.2. Point of Study Exit

All subjects enrolled in the clinical study shall be accounted for. An End of Study form is required for all study subjects and is completed following occurrence of any of these events:

- Subject completion of study participation
 - For subjects classified in the Responder Group, this is upon the completion of the 6 Month Visit.
 - For subjects classified in the Non-Responder Group, this is upon the completion of the 12 Month Visit.

- Subject withdrawal
- Subject death

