11.5.16. Final device settings and status

Print a copy of the Device Settings Report from the PRM for all subjects at the 6 Month Visit and clear the device counters as the final step. For non-responder subjects with at least 2 viable LV pacing vectors, it is required to turn on the LV MSP feature. The pacing chamber (BiV or LV only) is required to be the same as determined at the Enrollment Visit. All other programming settings are per investigator discretion.

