19.6. Risk to Benefit Rationale

The risks involved with subject participation in this study are the same as those for patients not participating in the study. The LV MSP feature will only be turned on in the study for subjects who are determined to be non-responders to conventional CRT therapy as defined in the protocol and may be turned off per physician discretion. Physicians should consider turning the LV MSP feature off if a subject's HF condition worsens. This study is designed to evaluate whether the LV MSP feature can improve clinical response to CRT in subjects who are not responders to conventional CRT.

20. Safety Reporting

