25.2. Definitions

Terms are defined in **Table 25.2-1**.

Table 25.2-1: Definitions

Term	Definition
Clinical Composite Score (CCS)	A method for evaluating heart therapies that unifies four outcomes of primary importance to clinicians: all-cause mortality, HF event, Patient Global Assessment, and New York Heart Association (NYHA) class.
Resonate family of CRT-D devices	As the next generation of BSC’s CRT-D devices, Resonate refers to all trademarked devices in this family of pulse generators, including RESONATE HF, RESONATE, VIGILANT, and MOMENTUM.
LV MSP feature related Complication	The LV MSP feature related adverse events will include, but are not limited to the following: 
 • Ventricular Tachyarrhythmia/Ventricular Fibrillation (VT/VF) • Loss of Capture • Phrenic Nerve Stimulation (PNS)

Table 25.2-1: Definitions

Term	Definition
	
 • Worsening HF
Conventional CRT	CRT with single-site LV pacing
Responder Group	Subjects with Improved CCS score at the 6 Month Visit.
Non-Responder Group	Subjects with Unchanged or Worsened CCS scores at the 6 Month Visit.
LV MSP Group	Subjects who have achieved at least 2 viable LV pacing vectors, have the LV MSP feature enabled, and with the percent of LV MSP pacing threshold of at least 93%
LV MSP Pacing	BiV pacing with the LV MSP On
LV MSP LV Only Pacing	LV only pacing with the LV MSP On
Viable LV Pacing Vector	
To determine if an LV pacing vector is considered viable, the following criteria are recommended:
 
 • The pacing impedance is not out-of-range per physician's programmed value • No presence of PNS - the pacing capture threshold (PCT) plus 3V of safety margin should be less than PNS threshold • LV PCT at $\leq 4.5V$ or demonstrated capture at $\leq 4.5V$

26. References

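### The plan does not say how the device is programmed in Improved-CCS subjects held on the non-responder path while an event awaits adjudication, and its sections can be read in opposite ways

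*Combined protocol and SAP*

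**What the plan says.** Section 11.5.5 defines the two classes by the score alone: "Responder: subjects with an Improved CCS score" and "Non-Responder: subjects with a Worsened or unchanged CCS score". Table 25.2-1 does the same for the groups. The Responder Group is "Subjects with Improved CCS score at the 6 Month Visit" and the Non-Responder Group is "Subjects with Unchanged or Worsened CCS scores at the 6 Month Visit".

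Section 11.5.5 then adds a holding rule. It says that anyone who has had "any hospitalization or IV therapy reported in the first 6 months will continue to be followed as a non-responder, regardless of the CCS". Where the CEC finds that the event was not heart failure and the subject belongs to the Responder Group, the subject leaves before the 12 Month Visit and is left out of the non-responder analysis. The section closes by placing non-responders in follow-up through the Non-Responder Group.

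Programming at the 6 Month Visit is set elsewhere. Section 11.5.16 states: "For non-responder subjects with at least 2 viable LV pacing vectors, it is required to turn on the LV MSP feature". Section 11.5.9 says the same under its heading on LV MSP status in the Non-Responder Group. Section 11.5.14 requires the feature to stay on until the 12 Month Visit. It names worsening symptoms as a reason for switching off, and asks for a rationale and a deviation in that case.

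Two other sections bear on the same subjects. Section 10.2, on the end of participation, states: "For subjects classified in the Responder Group, this is upon the completion of the 6 Month Visit". Section 19.6 states: "The LV MSP feature will only be turned on in the study for subjects who are determined to be non-responders". That sentence goes on to tie non-response to the protocol's own definition and to leave switching off to the physician.

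**The concern.** The holding rule is triggered by hospitalization or IV therapy for any cause. An event that the site itself counts as heart failure already makes the CCS Worsened under 11.5.1.4. What the holding rule adds is mainly the subject with an Improved CCS whose event the site did not count as heart failure.

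A site that follows 11.5.5 and then the programming sections would switch LV MSP on in that subject at the 6 Month Visit. A site that starts from Table 25.2-1 or 19.6 would not. The first site changes the pacing of someone who is improving on conventional CRT, outside the non-responder population that the synopsis names for the feature. If the CEC then rules that the event was not heart failure, the exit removes the subject from the non-responder analysis but does not undo the exposure.

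There is also a safety-reporting consequence. The primary safety set in Table 12.4-1 is non-responders with LV MSP on for any duration. An LV MSP-related complication in a subject later excluded as a responder may therefore not be counted.

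**Working it through.** **Sections side by side, for a subject with Improved CCS, a hospitalization not counted as heart failure by the site, and two viable vectors**

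| Section | Applied to this subject |
|---|---|
| 11.5.5, class definitions | Responder |
| Table 25.2-1 | Responder Group |
| 10.2 | Participation ends at the 6 Month Visit |
| 11.5.5, holding rule | Followed as a non-responder |
| 11.5.9, 11.5.14, 11.5.16 | LV MSP on to 12 months, if a non-responder for programming purposes |
| 19.6 | LV MSP only if determined to be a non-responder |
| 11.5.5, after the CEC rules not heart failure | Exits early, excluded from the non-responder analysis |

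No section defers programming until the CEC has ruled, exempts these subjects, or says what happens to the LV MSP setting when they exit. The attrition flowchart in the synopsis has no branch for them.

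**Timing.** The only limit stated in the protocol is that the exit comes before the 12 Month Visit. Section 20.4 allows 10 business days to report a serious adverse event and 60 calendar days for source documents. Events late in the first 6 months may therefore still be open at the 6 Month Visit, while earlier ones could be settled.

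**Planned flow (12.3 and the synopsis flowchart)**
- 586 × 0.90 = 527 at the 6 Month Visit
- 527 × 0.70 = 369 responders; 527 × 0.30 = 158 non-responders
- 158 × 0.85 = 134 non-responders with two viable vectors, hence LV MSP on
- 134 − 10 (exit) − 14 (LV pacing below 93%) = 110, the planned effectiveness sample

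The plan's figures reproduce.

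**Illustrative size.** Let h be the share of the 369 responders with a hospitalization or IV therapy that is not heart failure. The documents give no value, so h is an assumption. The 85% with two viable vectors is the plan's own figure.

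- Held on the path = 369 × h
- With LV MSP on = 369 × h × 0.85
- Share of all recipients = (369 × h × 0.85) / (369 × h × 0.85 + 134)

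| h | Held | LV MSP on | Share of all recipients |
|---|---|---|---|
| 5% | 18.5 | 15.7 | 15.7 / 149.7 = 10.5% |
| 10% | 36.9 | 31.4 | 31.4 / 165.4 = 19.0% |
| 15% | 55.4 | 47.0 | 47.0 / 181.0 = 26.0% |

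Each row assumes that no event is adjudicated before the 6 Month Visit and that every site follows the programming sections. The counts are thus near an upper bound for the given h.

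**The case against.** A reader might infer that the protocol flatly both requires and forbids LV MSP in these subjects. The text does not go that far. Section 11.5.5 does not mention LV MSP, and the requirement arises only by joining it to the programming sections. Those sections address non-responders, whom the definitions identify by CCS, and 11.5.9 already has some subjects followed on this path with the feature off. On that reading the holding rule extends follow-up and nothing more. On the other reading, being followed as a non-responder is itself a protocol definition, and 19.6 is met. Each reading is largely consistent within itself, so the defect is that the plan supports both. The second is still strained, because 11.5.5 itself accepts that such a subject may belong to the Responder Group.

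The holding rule also has a sound purpose. An Improved CCS requires freedom from heart failure events, so the status is provisional until the CEC rules, and holding the subject avoids releasing someone who proves to be a non-responder. That stands. It does not settle what the device should be doing in the meantime.

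Three further inferences should not be drawn:
- That the CEC has no deadline. Section 22.2 refers committee procedures to a charter that is not available here, so only the protocol's silence can be stated.
- That 19.6 proved untrue in practice. The documents are a plan and show nothing about how any site programmed a device.
- That these subjects would bear the full battery cost in 19.3 (an average of 6 weeks, up to 4.8 months). Those figures describe therapy from the 6 to the 12 Month Visit, and subjects who exit earlier would use less during the study.

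Section 19.6 also lets the physician switch the feature off. This limits the harm without removing it, since 11.5.14 makes switching off a deviation and the only reason it names does not fit an improving subject.

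**Conclusion.** The point holds as an unresolved conflict of reading. The plain combined reading of 11.5.5 with 11.5.9, 11.5.14 and 11.5.16 leads to LV MSP in Improved-CCS subjects, while the definitions, 10.2 and 19.6 point the other way. Programming during adjudication and at early exit is not stated.

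The conflict exists at any event rate above zero. Its size is unknown: about 16 to 47 subjects, or 10% to 26% of LV MSP recipients, rests on an assumed rate of 5% to 15% and on no adjudication before the 6 Month Visit. The planned effectiveness sample of 110 is not in question, because 11.5.5 excludes subjects found to be responders from the non-responder analysis. What is at stake is consistent treatment across sites, and whether complications in exposed responders are reported.

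**What to change.** 1. Reconcile 10.2, 11.5.5, 11.5.9, 11.5.14, 11.5.16, 19.6 and Table 25.2-1 so that one rule covers device programming for these subjects while the CEC decision is pending and at early exit. Which rule it should be is for the sponsor and investigators.
2. State in the protocol, or cite from the CEC charter, a review time for events in the first 6 months.
3. Report how many such subjects had LV MSP on, for how long, and any LV MSP-related complications, whether or not they fall in the primary safety set.

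The cost is protocol wording, some scheduling pressure on the CEC, and one listing. Section 11.7 already requires an Additional Visit record, with a rationale, when LV MSP is switched on or off, so much of the listing should need no new data.
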